5.2 Exclusion Criteria

1. Shared iCloud account
2. Shared AppleWatch

5.3 Recruitment

Apple Watch Series 1-4 users who telephone AppleCare about the Irregular Rhythm Notifications or ECG app and report having received an IRN or ECG app classification of atrial fibrillation or inconclusive on repeated measurement will be offered information about participation in the study. AppleCare provides technical support for Apple hardware, software, and services. For issues related to the IRN feature and ECG app, participants will be routed via telephone to an AppleCare advisor who is trained in handling technical questions and any medical complaints related to the use of the IRN feature and ECG app. Users who indicate interest in the study will be emailed a link to download and install the Study App. The Study App will determine study eligibility and enroll the participant in the study. If, 60 days after the

This document contains information that is privileged or confidential and may not be disclosed unless such disclosure is required by applicable laws and regulations. The information in this document is the property of Apple Inc. and may not be reproduced, published, or disclosed to others without written authorization from Apple Inc.

study opens, there is evidence that enrollment rates will not be adequate to meet enrollment goals for each subgroup, then alternative recruitment strategies may be employed to help reach recruitment goals.

This document contains information that is privileged or confidential and may not be disclosed unless such disclosure is required by applicable laws and regulations. The information in this document is the property of Apple Inc. and may not be reproduced, published, or disclosed to others without written authorization from Apple Inc.

6.0 STUDY DEVICES

Device 1 Name: Irregular Rhythm Notification feature

The Irregular Rhythm Notification Feature is a software-only, FDA-cleared, mobile medical application that is intended to be used with the Apple Watch. The feature analyzes pulse rate data to identify episodes of irregular heart rhythms suggestive of AFib and provides a notification to the user. The feature is intended for over-the-counter (OTC) use. It is not intended to provide a notification on every episode of irregular rhythm suggestive of AFib and the absence of a notification is not intended to indicate no disease process is present; rather the feature is intended to opportunistically surface a notification of possible AFib when sufficient data are available for analysis. These data are only captured when the user is still. Along with the user's risk factors, the feature can be used to supplement the decision for AFib screening. The feature is not intended to replace traditional methods of diagnosis or treatment.

Device 2 Name: ECG app

The ECG app is a software-only, FDA-cleared, mobile medical application intended for use with the Apple Watch to create, record, store, transfer, and display a single channel electrocardiogram (ECG) similar to a Lead I ECG. The ECG app determines the presence of atrial fibrillation (AFib) or sinus rhythm on a classifiable waveform. The ECG app is not recommended for users with known arrhythmias other than atrial fibrillation.

The ECG app is intended for over-the-counter (OTC) use. The ECG data displayed by the ECG app is intended for informational use only. The user is not intended to interpret or take clinical action based on the device output without consultation of a qualified healthcare professional. The ECG waveform is meant to supplement rhythm classification for the purposes of discriminating AFib from normal sinus rhythm and not intended to replace traditional methods of diagnosis or treatment.

This document contains information that is privileged or confidential and may not be disclosed unless such disclosure is required by applicable laws and regulations. The information in this document is the property of Apple Inc. and may not be reproduced, published, or disclosed to others without written authorization from Apple Inc.

7.0 STUDY PROCEDURES

Time (days)	Event
0	Study Opens
60	Interim check of enrollment
180	End Enrollment
270	Study Closes (latest date for completion of PRO questionnaire)
270+	Analyses

Table 1. Study Timeline

7.1 Eligibility Determination and Enrollment

The potential participant will first download the Apple Heart Study 1.2 App. The app will automatically ensure compatibility with the iPhone iOS version and Watch version. If compatible, the participant will be able to continue forward in the app. An overview of the study will be displayed in the app.

The participant will then advance to a screen for study enrollment, where they will confirm whether they meet general participation requirements. The participant will be asked questions based on study inclusion and exclusion criteria. The app will automatically determine eligibility based on the responses provided. If the participant is determined to be eligible, they will initiate the consenting process with an in-app consent and authorization form to be read and signed if they agree to participate.

Participants will be able to enroll between STUDY START DATE and END OF ENROLLMENT (STUDY START DATE + 6 months).

On END OF ENROLLMENT, enrollment will close. The study period will end on END OF ENROLLMENT + 60.

A 15-day PRO will become available 15 days after enrollment, no later than END OF ENROLLMENT + 15. A 60-day PRO will become available 60 days after enrollment, no later than END OF ENROLLMENT + 60. All PROs will be due by end of study on END OF ENROLLMENT + 90. After this date, all monitoring will end, the Study Telehealth Provider line will be closed and no further data will be collected.

This document contains information that is privileged or confidential and may not be disclosed unless such disclosure is required by applicable laws and regulations. The information in this document is the property of Apple Inc. and may not be reproduced, published, or disclosed to others without written authorization from Apple Inc.

Enrollment may be terminated early if more than 400 participants receiving an IRN and more than 400 participants using the ECG app are diagnosed with AF by ECG patch. Enrollment will be reviewed at STUDY START DATE + 60 days. If enrollment in each of the study subgroups outlined in the objectives appears that it will not achieve a sufficient number of subjects to meet study goals, we will enhance recruitment by targeting recruitment strategies to the group(s) of participants at risk for failing to meet study goals or extend the duration of enrollment.

7.2 Enrollment: Consent, Baseline Demographics and Medical History Collection

The Apple Heart Study 1.2 is an app-based research study utilizing the iOS platform. As in other mobile-mediated research studies, the informed consent process in the study is conducted remotely in a completely self-administered setting with no required physical contact with the research team prior to consent and enrollment.

The approach to informed consent for the study has been adapted accordingly to ensure the ethical requirement of informedness, i.e. that participants are adequately informed about the research before participation, is met. Potential candidates as well as enrolled participants will be able to contact a study hotline (available 24/7 at [name]) anytime and have the ability to ask questions and request clarifications at any time prior to or during the study. This hotline will be open from the study start date until study closure.

Participants who successfully pass the eligibility criteria will be directed to a page requesting their consent to participate. Participants will be asked to read and sign the study informed consent and authorization document within the app if they agree and are willing to participate. A copy of the signed study consent and authorization document will be available for review and download to the participant via the app.

After consenting to participate, the participant will be directed to complete a questionnaire to collect self-reported baseline demographics, medical history, and health status.

A participant will be considered enrolled if the participant has consented and completed onboarding questionnaires.

7.3 Procedures for Study Visit #1

7.3.1 Study Telehealth Provider

American Well (Boston, MA) is a healthcare technology company that developed the Telehealth platform being used to support study visits. The American Well technology supports mobile-based interactions between participants and providers during the study, in

This document contains information that is privileged or confidential and may not be disclosed unless such disclosure is required by applicable laws and regulations. The information in this document is the property of Apple Inc. and may not be reproduced, published, or disclosed to others without written authorization from Apple Inc.

which both the participant and provider can see and hear each other through American Well's proprietary videoconferencing capabilities. Virtual visits can be conducted using a wireless or network connection, meaning a study participant can initiate a visit from anywhere in the 50 United States or District of Columbia. American Well's platforms are a SaaS (Software as a Service) offering—this means all operational hardware and support software is housed and maintained within American Well data centers and is serviced by the American Well Hosting Operations department. American Well is a PCI-compliant and is designed to meet HIPAA security requirements, HITRUST-certified, federally recognized security platform.

The Online Care Group (OCG) is American Well's clinical partner. OCG providers are responsible for conducting the study required assessments during study visits. All OCG physicians are licensed, board certified, have 10-15 years of experience in a brick-and-mortar practice, and have undergone a vigorous training on American Well's platform. Additionally, the OCG has an internal credentialing process that meets all standards as dictated by the National Committee for Quality Assurance. The OCG's staff physician-led credentialing committee (comprised of a chief medical officer, staff physician, and director of behavioral health) reviews and approves all practitioners before they are permitted to practice on the American Well System.

Study Telehealth Provider Team, a term used throughout this protocol, relates to physicians from the OCG, Quality, Customer Support (Level 1 agents operating the 24-hour hotline and Level 2), and the Network Operations Center (NOC) staff who will coordinate visits and facilitate the communication of patch report results and clinical summaries to the participant. All these groups provide services through American Well platform.

7.3.2 Study Telehealth Provider Visit #1

The Study App will provide a button for the participant to connect with the Study Telehealth Provider. The first connection with the Study Telehealth Provider will constitute Study Visit #1.

After the participant connects with the Study Telehealth Provider team, they will undergo a study visit. The participant will be asked about cardiovascular clinical signs and symptoms. If the Study Telehealth Provider concludes that the participant has a medical emergency, the Study Telehealth Provider will follow its emergency protocol and either instruct the participant and/or a family member, if available, to call emergency medical services (EMS) or will call on the participant's behalf if the participant and/or a family member are unable to contact EMS. Participants with a medical emergency will not be prescribed an ePatch.

Once emergency symptoms have been ruled out, the telehealth clinician will perform an abbreviated review of medical history and perform a virtual review of physical symptoms. The telehealth provider will also confirm which of the following the participant received: Irregular

This document contains information that is privileged or confidential and may not be disclosed unless such disclosure is required by applicable laws and regulations. The information in this document is the property of Apple Inc. and may not be reproduced, published, or disclosed to others without written authorization from Apple Inc.

Rhythm Notification, ECG app classification of AF, or ECG app classification of inconclusive. If the participant cannot confirm having received any of the above notifications or classifications, the Study Telehealth Provider will not prescribe an ePatch. The information obtained will assure that the Study Telehealth Provider Data Collection variables [see 7.3.3 Study Telehealth Provider Data Collection] are obtained.

The visit summary will be made available to the participant and also to participant's physician or health care provider, if the participant provides the Study Telehealth Provider information of participant's physician and permission to send that physician a copy of the report. Any referral visits will be conducted outside of the study, at the discretion of the participant, and at the cost of the participant.

The Study Telehealth Provider will provide the participant information about the ePatch, answer any questions the participant might have, and contact BioTelemetry to initiate the order and shipment of the ambulatory ECG monitor (ePatch).

7.3.3 Study Telehealth Provider Data Collection – Visit #1

The following data elements will be collected during the study visit:

1. Demographics
2. IRN or ECG app results
3. Past medical history
4. Medications
5. Symptoms
6. Clinical assessment
7. Complaints or adverse events

7.4 Procedures for Ambulatory ECG Patch

7.4.1 BioTelemetry Flow

1. The Study Telehealth Provider will order the ECG patch from BioTelemetry and communicate information necessary for mailing ECG patch and study data management to BioTelemetry.
2. If the participant did not have Study Visit #1 within 30 days of enrollment, participant will still be able to receive a patch monitor and continue with study procedures including PROs, but they will not be included in the primary analyses.
3. BioTelemetry will mail the ambulatory ECG monitor to the participant.

This document contains information that is privileged or confidential and may not be disclosed unless such disclosure is required by applicable laws and regulations. The information in this document is the property of Apple Inc. and may not be reproduced, published, or disclosed to others without written authorization from Apple Inc.

4. The participant will wear the ambulatory ECG monitor for up to 7 days and mail the monitor back to BioTelemetry.
5. After the ambulatory ECG monitor has been worn by the participant for up to 7 days and returned back to BioTelemetry, BioTelemetry will perform data extraction and an initial technical read of the ambulatory ECG findings by trained ECG technicians. The ECG technician review will determine if the participant has any serious or potentially life-threatening abnormality. Although rare, this includes atrial fibrillation with sustained rapid ventricular rates, sustained ventricular tachycardia or ventricular fibrillation, high-degree heart block, and long pauses. If one of these urgent arrhythmias is identified, then the participant will be contacted and directed to local emergency care or advised how to seek local emergency care. Best attempt will be made to send the ECG report to participant's emergency care provider. After confirmation that a participant's ambulatory ECG data does not have any of these urgent arrhythmias, the ambulatory ECG study will be processed into the adjudication workflow. The adjudication workflow is described in a separate charter.
6. The adjudication process will result in generation of a final adjudicated report.
7. Once the adjudicated report is complete, it will be issued to the Study Telehealth Provider.

7.4.2 Procedures for ECG patch wear

The BioTelemetry ePatch Monitor will be used for ambulatory ECG monitoring. The battery life with a single channel recording is 7 days. The participant will be instructed to wear the ePatch for up to 7 days. However, the data collected from a participant will be considered adequate for a participant with a minimum analyzable time of 1 hour.

BioTelemetry will send participants, via courier, an ambulatory ECG monitoring kit containing one sensor and two adhesive patches. If the adhesive patch is no longer functional, the sensor

This document contains information that is privileged or confidential and may not be disclosed unless such disclosure is required by applicable laws and regulations. The information in this document is the property of Apple Inc. and may not be reproduced, published, or disclosed to others without written authorization from Apple Inc.

can be moved to the backup adhesive patch. At the end of the recording period, the participant will be required to mail the monitor back to BioTelemetry using the supplied prepaid mailer.

In the event it is discovered that the participant never received the ePatch due to a shipping error or became lost in transit, then BioTelemetry will issue a second ePatch to that participant. Any subsequent loss of ePatches will not be replaced.

Approximately 14-20 days after enrollment it is expected that most participants will have completed wearing the patch for up to 7 days and will have returned the patch to BioTelemetry via a provided tracked USPS mailer. The ambulatory ECG monitor should be received by BioTelemetry within 45 days from enrollment. Those who return patches beyond 45 days after enrollment or do not begin wearing their patch within 14 days of patch shipment will be included in the fall-out subgroup, however they will still be eligible for a follow-up visit with the Study Telehealth Provider. Those who never return the ambulatory ECG monitor will also be placed in the fall-out subgroup.

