Participants with urgent symptoms (chest pain, shortness of breath, fainting/losing consciousness) will be directed to an urgent care clinic or emergency room for medical evaluation. For participants with non-urgent symptoms, the Study Telehealth Provider will order an ambulatory ECG monitor (i.e. an ePatch) from BioTelemetry. Participants will be expected to contact the Study Telehealth Provider within 30 days of enrollment. Study participants will be reminded to initiate Study Visit #1 with reminders via email and phone calls if needed. Participants who call after 30 days will still be able to obtain an ePatch and undergo remaining study procedures, but may not be included in all analyses.

The participants will be mailed the ambulatory ECG monitor, which the participant will then be requested to wear for up to 7 days. The minimum analyzable time acceptable for primary

This document contains information that is privileged or confidential and may not be disclosed unless such disclosure is required by applicable laws and regulations. The information in this document is the property of Apple Inc. and may not be reproduced, published, or disclosed to others without written authorization from Apple Inc.

analysis is one hour. Participants with the ECG app will be asked to take an ECG app recording at least 2 times each day while wearing the ePatch, as well as after receiving an irregular rhythm notification. The participant will then mail the ambulatory ECG monitor back to BioTelemetry, which will generate a standard technical report that will be read by BioTelemetry's technical readers. The report will be adjudicated by two board-certified clinicians, and a final report will be made available to the Study Telehealth Provider by BioTelemetry.

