3. ANALYSIS SETS

The Full Analysis Set (FAS) will consist of all enrolled participants who complete the informed consent process. This analysis set will be used to summarize subject demographics, medical history, adverse events, self-reported health status, diagnosis, and contact with the health care provider.

The ePatch Eligibility Analysis Set (EEAS) will consist of those in the FAS deemed eligible to receive an ePatch at Study Visit #1. This analysis set will be used to assess Objective 2a.

The ePatch Analysis Set (EAS) will consist of all those in the EEAS who receive and return an ePatch with at least 1 hour of usable data and who do not belong to the Fallout Subgroup. This analysis set will be used to assess Objectives 1a, 1b, and 2b and 2c. We will repeat these analyses in the EEAS as a sensitivity analysis using appropriate methods for handling missing data.

The Fallout Subgroup Analysis Set (FOG) will consist of participants who enroll and complete the informed consent process but otherwise do not complete the study. Reasons for study incompleteness include; failure to contact Study Telehealth Provider within 30 days of enrollment, being deemed ineligible at Study Visit #1 for ePatch wear due to emergent symptoms, ePatch not returned within 45 days of enrollment, failure to start wearing ePatch within 14 days of shipment, unable to verify at Study Visit #1 a study eligible IRN or ECG-app notification, study withdrawal (i.e., withdrawal of consent), or lost to follow-up (i.e., death). We will present demographic and medical history information for this analysis set.

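### At their outer limits the 30-, 14- and 7-day windows reach day 51, past the 45-day patch return limit, so a participant who keeps the earlier rules can still be dropped from the primary analysis set

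*Combined protocol and SAP*

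**What the plan says.** Four time limits govern the patch, and they run from different starting points.

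- **Visit #1, from enrollment.** Protocol 4.1: "Participants will be expected to contact the Study Telehealth Provider within 30 days of enrollment". Protocol 7.4.1 gives the consequence of missing it: "If the participant did not have Study Visit #1 within 30 days of enrollment, participant will still be able to receive a patch monitor", "but they will not be included in the primary analyses". Under Protocol 7.3.2 the patch is ordered at this visit, so it cannot ship earlier.
- **Start of wear, from shipment, and return, from enrollment.** Protocol 7.4.2 assigns to the fall-out subgroup "Those who return patches beyond 45 days after enrollment or do not begin wearing their patch within 14 days of patch shipment". SAP 3 lists the same two reasons: "ePatch not returned within 45 days of enrollment, failure to start wearing ePatch within 14 days of shipment".
- **Wear.** Protocol 7.4.1: "The participant will wear the ambulatory ECG monitor for up to 7 days and mail the monitor back to BioTelemetry". One hour of analyzable data is enough for the EAS.
- **Replacement.** If a patch is lost in shipping, Protocol 7.4.2 says "then BioTelemetry will issue a second ePatch to that participant". Nothing is said about adjusting the 45-day limit.

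Protocol 10.1 and SAP 3 exclude the fall-out subgroup from the EAS. Protocol 10.4 and SAP 4.6 class a patch that is not back within 45 days as missing data, to be handled by methods such as multiple imputation when the analyses are repeated in the ePatch-eligible set (EEAS). Protocol 7.4.2 expects most participants to have worn and returned the patch about 14–20 days after enrollment.

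**The concern.** A participant can satisfy the 30-day rule and the 14-day rule, wear the patch for the full 7 days, mail it at once, and still pass day 45. Two outcomes are then possible. Either the participant leaves the EAS with a usable ECG recording in hand, or wear is cut short to meet the deadline. SAP 4.7 says wear shorter than 7 days will likely contribute to underestimating the AF proportion. Both outcomes select on how quickly a participant acts, which has no stated link to the validity of the recording.

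The missing-data rule carries the same problem into the sensitivity analysis. A recording that arrives on day 46 is an observed primary outcome, yet the plan would treat it as missing and impute it.

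**Working it through.** **Inputs.** Latest Visit #1 that still counts: V = 30 (Protocol 7.4.1). Start window: d = 14 days from shipment (Protocol 7.4.2, SAP 3). Wear: w = 7 days at most (Protocol 7.4.1, 7.4.2). Return limit: day 45. The time from order to shipment (s) and the return transit (r) are not stated. I take s = r = 0 as the case most favourable to the plan, then assume s = 0–3 and r = 0–5 days. If return means mailing and not receipt, r = 0.

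The 45-day limit is given as a rule without derivation, so there is no plan figure to reproduce.

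**Day of return** = V + s + d + w + r.

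1. Outer limits, zero transit: 30 + 0 + 14 + 7 + 0 = 51, and 51 − 45 = 6 days over.
2. Latest Visit #1 that allows the full start window and 7-day wear: 45 − 14 − 7 = day 24.
3. Visit #1 on day 30 with 7-day wear: start within 45 − 30 − 7 = 8 days of shipment, not 14.
4. Both windows fully used: 30 + 14 = day 44, which leaves 45 − 44 = 1 day for wear.

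**With assumed transit (s = 0–3, r = 0–5).**

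- Day of return at the outer limits: 51 to 51 + 3 + 5 = 59, or 6 to 14 days over.
- Latest Visit #1 for the full windows: day 24 down to 24 − 8 = 16.
- Start allowance after a day-30 visit: 8 down to 8 − 8 = 0 days.

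The meaning of return matters. Take s = 1. If mailing counts (r = 0), the latest Visit #1 is day 23 and the start allowance 7 days. If receipt counts and r = 3, they are day 20 and 4 days. Protocol 7.4.2 says the monitor should be received by day 45, whereas SAP 1.2 has the participant mail it back within 45 days.

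**How much of the allowed range conflicts.** Visit #1 on days 0–30 and start on days 0–14 after shipment give 31 × 15 = 465 combinations. With 7-day wear and zero transit, 21 overrun (21/465 = 4.5%). With s = 2 and r = 3, 66 overrun (66/465 = 14%). These are shares of day combinations, not of participants.

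**Replacement patch.** If the second shipment goes out L days after the first and the participant then uses the full start window and 7-day wear, the zero-transit total becomes 51 + L, while the limit stays at 45. The text does not say which shipment starts the 14-day window.

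**Visit #2.** Protocol 7.6 expects this visit on days 15–45, after receipt and adjudication. A patch received on day 45 fits only if adjudication and the visit happen the same day.

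**The case against.** The limits can be read as separate cut-offs under an overall cap, with no promise that each maximum may be used in turn. Wear is a maximum of 7 days and one hour suffices, so with zero transit even a participant who starts on day 44 can enter the EAS. The plan expects most to be done by day 14–20, allows for about 35% attrition, repeats the analyses in the EEAS, varies the minimum wear time from 6 hours to 5 days, describes the fall-out subgroup, and acknowledges short-wear and missing-patch bias. All of that stands, and it limits the size of the problem.

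It does not remove it. The attrition allowance protects precision but not against selection. The wear-time analyses never vary the 45-day rule. The EEAS analysis treats the late recording as missing.

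Three stronger readings are tempting, and the documents do not support them.

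- A reader might infer that the windows can never all be met. They can, by anyone with an early enough Visit #1 or patch start.
- A reader might infer that the 45-day limit alone decides EAS membership. Each rule excludes independently: Visit #1 on day 31 with return on day 42 fails only the 30-day rule, and Visit #1 on day 5 with a start 17 days after shipment and return by day 32 fails only the 14-day rule.
- A reader might infer that every Visit #1 after day 24 is in conflict. At zero transit that holds only if enough of the start window is also used.

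**Conclusion.** The point holds as an inconsistency at the outer limits. The stated maxima reach day 51 against a limit of day 45, and this needs no assumption about transit, nor about whether return means mailing or receipt. Under the assumed transit times the overrun is 6–14 days. A participant who meets the 30- and 14-day rules and wears the patch for 7 days can be excluded from the EAS, and one whose first patch was lost in shipping gets no allowance.

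The number affected cannot be derived from the documents. It is probably small, given the expected completion by day 14–20. The direction of any exclusion bias is unknown; SAP 4.7 itself says that excluding participants without patch data may move the estimates either way. Shortened wear would tend to lower the AF proportion. The clearest analytic fault is that an observed primary outcome is discarded from the EAS and then imputed in the EEAS. This should be corrected, but nothing in the documents shows that it would materially change the primary estimates.

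**What to change.** 1. Reconcile the 30-, 14-, 7- and 45-day limits in Protocol 7.4.2, 7.12 and 10.4 and in SAP 3 and 4.6, together with the Visit #2 timing in Protocol 7.6. Define return as either mailing or receipt, and use that meaning in Protocol 7.4.2 and SAP 1.2. State which shipment starts the clock when a replacement is sent.
2. For analysis, do not exclude a participant from the EAS solely for the 45-day limit if the 30-day and 14-day rules were met (the latter counted from shipment of the patch actually worn), the patch has at least 1 hour of usable data, and it arrives before study close. Name the closing date, since Protocol 7.1 uses both END OF ENROLLMENT + 60 and + 90. Say also how a patch is handled when it arrives after the participant's own participation has ended.
3. At minimum, use such late results as observed data in the EEAS sensitivity analysis and not as missing.

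The cost is protocol and SAP wording. Shipment dates are already needed for the 14-day rule. The downsides are that some results and second visits come later, and that some patches are worn further from the initial notification, a gap that SAP 4.7 also links to underestimating AF. Under the assumed transit times, the slowest case without a replacement returns by day 59; a replacement could be later.
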